2.4.2 Comparative study of Digital Health Inequality

A cross sectional comparative study will contrast digital health participation of people with intellectual disabilities to a reference group people without disabilities.

Comparator

A reference group of 200 participants without disabilities will be recruited across the study sites via local advertisement and social media. This referent group will concurrently complete the same Digital Health Participation survey online via Qualtrics. A referent sample of 200 will allow detection of a group difference, $d=0.2812$ (small-medium effect) at 90% power, 2:1 group ratio, and $\alpha=0.05$. Sample size calculations were conducted using G*Power 3.1.9.7. Our overall planned accrual rate for the referent group is 25-30 participants per month across the four study sites (6-8 per site) over seven months to reach our aim of a final sample size of 200.

Primary outcome

Digital health participation levels as developed from the work in WP1 will be used as the primary outcome measure.

Secondary outcome

Level of mental and physical wellbeing will be measured using the EQ5 (Herdman *et al.* 2011).

Comparative study statistical analysis

Descriptive analysis of levels and frequency of digital health participation of the groups (N=600). Between group comparison using general linear model (GLM) of digital health participation of people with intellectual disabilities.

The study will use propensity score weighting (inverse probability weights) to reduce the bias due to confounding variables and ensure sufficient balance across groups. The propensity scores will be generated on the basis of the following variables: geographic region, sex, age band, ethnicity, and deprivation index. In the event that models including the probability weights do not converge, we will explore other approaches to resolve (i.e. direct adjustment as the number of covariates is relatively small).

We will test whether the data is missing completely at random (MCAR) using Little's test for missing completely-at-random (MAR) (Little, 1988) if more than 10% of data is missing. Data is MCAR if the test is not significant, meaning the estimates will be sufficiently unbiased to not need any adjustments. If data is found to be MAR, GLMs will use multiple imputation via chained equations and up to 10 imputation sets will be generated, then pooled following Rubin's Rules (following Granger *et al.*, 2019). All parameter estimates will be reported with 95% confidence intervals. Both imputed and complete case model estimates will be reported for comparison.

A more detailed Statistical Analysis Plan (SAP) will be developed once WP1 is completed and the digital health participation survey which will be administered as part of WP2 is developed.

2.5 Digital Diary Study of Digital Health Participation (Months 14-16 and 24-32) - Work Package 3 (WP3).

To gain a deeper understanding of how digital health participation operates in the lives of people with intellectual disabilities, WP3 employs principles used in digital ethnographic research. This prioritises prolonged collection of rich, unstructured data through observations and accounts of participants (Hammersely, 2019) in contexts and environments which are predominantly digital (Jensen *et al.*, 2022; Pink *et al.*, 2016). Qualitative digital diaries offer a useful way to explore everyday experiences (Volpe, 2019) by utilising the benefits 'new mobilities' technology offers, enabling the ability to record textual, visual or digital diary information that is located in both time and space (Shellen & Urry, 2006).

We will conduct a digital diary study using tablets housing the ArcGIS software package (Jung & Elwood, 2020), which contains digital storytelling software and story mapping. ArcGIS enables generation of verbal, visual and survey data linked to specific community places. Real-time ArcGIS demographic, verbal, visual and narrative data generation about experiences, thoughts and feelings about using the technology in relation to their health will be gathered from participants, with support and prompting provided weekly by RAs and co-researchers. Concurrent to WP2 accessible 'easy-read' study materials will be developed.

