2.3.4 Scale Construction

Preliminary scale items will be shared in two co-creation workshops, one with people with intellectual disabilities and another with carers, to develop and work towards reaching consensus (Kooijmans *et al.*, 2022). From these, a long list of items will be generated for the Digital Health Participation Survey (self/supported completion) and Carer Proxy Digital Health Participation Survey. Items in these two measures will mirror each other with the latter containing third person rather than first person text. This measure of digital health participation will comprise: (i) Digital participation: access and use; skills and literacy; self-efficacy; (ii) Support for digital participation; (iii) Health literacy: functional; interactional; critical decision-making; (iv) Frequency and success of engagement in digital health activity (e.g. information seeking, video-consultation, health appointment and communications, use of digital health monitoring devices); (v) Additional inductively derived aspects of digital health participation which do not readily fit with the utilised frameworks. Piloting of the survey will occur with focus group participants prior to roll out in WP2.

A manual for the finalised scales will be developed. This will detail administration for people with intellectual disabilities from independent self-completion, through differing levels of support needs through to full proxy completion for participants with higher support needs, for example, those who are minimally verbal or have profound intellectual and multiple disabilities. Guidance on decision making regarding whether independent, supported or proxy completion is most appropriate will be included within the manual. This decision will be based on level of support needs, literacy, information processing and comprehension considerations. This will enable the measure to be applicable to all people with intellectual disabilities addressing the considerable heterogeneity within this population.

In addition, filtered administration logic will be developed, whereby initial screening by particular overarching questions can remove the need to subsequently answer sub-questions. This will both to reduce participant burden and administration time.

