2.4.1 Longitudinal Survey Study

The digital participation survey (Proxy or Self/supported completion as appropriate) will be administered to a convenience sample of 400 people with intellectual disabilities at two time points eight months apart (+/-1 month). This sample size will enable digital health participation for people with intellectual disabilities to be adequately understood across the breadth and heterogeneity inherent in this population. It will also enable a sufficiently powered analysis to identify moderate effect sizes in relation to predictors of digital health participation.

Survey sampling & recruitment

Adults with a diagnosis of intellectual disabilities and the family and paid carers (as proxy participants for people with higher support needs) are the target population. Taking a whole population approach, and to increase geographical diversity, a self-selecting sample of 400 adults with intellectual disabilities will be recruited equally from the four study sites.

Recruitment will be facilitated by partner organisations with established groups of people with intellectual disabilities and links with additional community groups and agencies which contain under-represented groups of people with intellectual disabilities. Birmingham Community Healthcare NHS Foundation Trust will also act as a recruitment centre. Our overall planned accrual rate is 50-60 participants per month across the four study sites (12-15 per site) over seven months to reach our aim of a final sample size of 400 (Note we expect some of the 60 participants from WP1 to participate in WP2 and WP3).

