Partner organisations will ensure adequate oversampling to offset participant drop out. The organisations will also support sample replenishment in the case of non-completion of the survey at time 1. Levels of dropout in longitudinal studies with individuals with intellectual disabilities is approximated at 13% (McCarron *et al.*, 2020); however, we will conservatively allow for up to 15% via oversampling (McCarron *et al.*, 2020). To ensure inclusion of under-represented groups (e.g. people with intellectual disabilities from: ethnic minority/global majority groups, with autism, who are older, and who have underlying physical health problems) and groups more at risk of digital exclusion (older; unemployed; living in group settings supported by paid staff; people with greater support needs (via carers) (Anrijs *et al.*, 2022), sample characteristics will be reviewed after 25% of initial survey data collection has been achieved. If insufficient at initial recruitment, a purposive/targeted sampling strategy, facilitated by partner organisations, will be implemented to ensure adequacy of representation. This review process will be repeated once 75% of initial survey data collection is complete.

Longitudinal survey data collection

Prior to data collection, participants and their carers will be invited to attend online training workshops provided within the project to support the survey data collection (Work package 2). Training will be provided by the CI and site/regional PIs alongside the RAs and the CRs with intellectual disabilities.

Participants will choose their preferred modality for survey completion (Paper-based, online completion (housed on Qualtrics), telephone completion, face-to-face completion as an interview with the geographically closest researcher or a known carer). Where appropriate, the survey will be administered by RAs and CR at each study site. Self and carer supported completion will also be offered for data collection. Survey methods are viable for use with people with intellectual disabilities and have been used successfully by applicants previously and in recent large-scale studies (e.g. Caton *et al.*, 2022). Guidance on completion will be

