provided in the manual with individualised support offered by RAs and co-researchers on an as needed/requested basis. The manual will provide guidance on deciding whether independent completion, supported completion or, proxy completion is most appropriate. The survey digitally housed (Qualtrics), printed versions of the survey will also be available if requested for subsequent entry by RAs. Carers proxy completing the survey will also be offered the same range of completion options (Paper-based, online completion (housed on Qualtrics), telephone completion, face-to-face completion as an interview with a researcher).

The survey will comprise: (i) The Digital Health Participation Survey developed in WP1; (ii) General ICT Use and Access (Anrijs *et al.*, 2022); (iii) Physical and Mental Wellbeing (EQ-5-3L, (Herdman *et al.*, 2011)); (iv) Salient Demographic (Gathered from participants in accordance with PROGRESS-plus criteria) (Oliver *et al.*, 2008; O'Neill *et al.*, 2014) and Background information (Current and historical health conditions, ongoing health involvement, day activities, levels of support need, literacy and communication, level of cognitive impairment and postcode to enable gathering of deprivation indices).

Longitudinal survey statistical analysis

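### Referents can answer only online while the intellectual-disability group can also answer offline, so adults with little or no digital access are kept out of one side of a comparison of digital participation

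*Protocol*

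**What the plan says.** **Referents.** Protocol section 2.4.2 (Comparator) says the reference group of 200 "will be recruited across the study sites via local advertisement and social media". It continues: "This referent group will concurrently complete the same Digital Health Participation survey online via Qualtrics". No paper, telephone, face-to-face or supported option is described for them.

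**People with intellectual disabilities.** Section 2.4.1 (data collection) says: "Participants will choose their preferred modality for survey completion (Paper-based, online completion (housed on Qualtrics), telephone completion, face-to-face completion as an interview", with a researcher or a known carer. It adds: "Carers proxy completing the survey will also be offered the same range of completion options". On sampling, the same section says: "Recruitment will be facilitated by partner organisations with established groups of people with intellectual disabilities", and an NHS trust also recruits. The make-up of this sample is reviewed at 25% and again at 75% of initial data collection, with targeted sampling if needed, so that it includes "groups more at risk of digital exclusion (older; unemployed; living in group settings supported by paid staff", along with people with greater support needs. No such review is set for referents.

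**Outcome and adjustment.** Section 2.4.2 states: "Digital health participation levels as developed from the work in WP1 will be used as the primary outcome measure". Section 2.3.4 lists the content of that measure, beginning "i) Digital participation: access and use; skills and literacy; self-efficacy". The propensity score in 2.4.2 is built from five variables: region, sex, age band, ethnicity and deprivation.

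**The concern.** Being able and willing to fill in an online form is a condition of entry for referents. Being online is also part of what the outcome measures. An adult without intellectual disabilities who is offline, and would score low, cannot enter the referent group. An offline adult with intellectual disabilities can enter the other group and is looked for. Entry to one arm therefore depends on the outcome, and entry to the other does not do so in the same way.

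The comparison of levels between the groups is objective v, and inequality is part of the study's primary aim. If the referent mean is too high, the reported inequality is too large. The fault lies in recruitment and data collection, so a later analysis plan cannot recover people who were never sampled.

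**Working it through.** **1. The plan's own figure.** Inputs from 2.4.2: 200 referents, 400 people with intellectual disabilities, alpha 0.05, 90% power, d = 0.2812. The standard error of a standardised difference is √(1/200 + 1/400) = √0.0075 = 0.0866. The normal approximation gives (1.960 + 1.282) × 0.0866 = 0.281. The noncentral t with 598 degrees of freedom gives a detectable d of 0.2812 and power of 90.0%, two-sided. The protocol does not state sidedness; a one-sided test would give 0.254. The stated figure is reproduced as two-sided. It concerns precision and does not bear on bias, but it gives a scale.

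**2. Who can enter each group.**

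| | Referents (2.4.2) | Intellectual-disability group (2.4.1) |
|---|---|---|
| Recruitment | Local advertisement, social media | Partner organisations, NHS trust |
| Completion | Online | Paper, online, telephone, face-to-face |
| Proxy | None described | Yes, same modes |
| Check for digitally excluded people | None described | At 25% and 75% |

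**3. Size of the shift.** Let q be the share of the referent population that an online-only route cannot reach, and δ the amount, in SD, by which that share scores below the rest. The population mean is (1 − q) × online mean + q × (online mean − δ), so the online mean exceeds it by q × δ. Neither q nor δ is in the protocol; the values below are assumptions. The last column is the chance of a significant result when there is no true difference (two-sided noncentral t, 200 against 400). It assumes an unweighted comparison with no offset from the other group.

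| q | δ (SD) | Shift q × δ (SD) | Shift ÷ 0.2812 | Rejection rate, nominal 5% |
|---|---|---|---|---|
| 2% | 1 | 0.02 | 7% | 5.6% |
| 5% | 1 | 0.05 | 18% | 8.9% |
| 10% | 1 | 0.10 | 36% | 21% |
| 10% | 1.5 | 0.15 | 53% | 41% |
| 15% | 2 | 0.30 | 107% | 93% |

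**4. What the planned adjustment can do.** Weighting redistributes referents who are already online. Where digital use varies with age band or deprivation, it can remove part of the shift; what remains is the shortfall within strata. It cannot supply offline referents. Adding internet access to the score would not help: there would be few or no offline referents to weight up, and it would adjust away part of the outcome. Multiple imputation fills in missing answers from participants, not people outside the sample.

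**The case against.** Several points on the other side stand.

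- **Confounding is not complete.** A reader might infer that mode and reporter are wholly confounded with group. The documents do not support that. Sections 2.3.4 and 2.4.1 provide for independent and online completion by people with intellectual disabilities, so the groups overlap among online self-completers. The confounding is strong, not total. Proxy reporting could not be matched anyway, because section 3.2.1 requires referents to have capacity to consent.
- **The other sample is selected too.** It is self-selecting, comes largely through advocacy organisations, and is invited to online training before data collection. That could raise its mean and offset part of the referent inflation. Pure mode and proxy effects could go either way.
- **The size is assumed.** The upper end of the range needs both extreme inputs together, and no allowance is made for weighting. A reader might take 107% to mean that the whole finding could be an artefact. It does not mean that: 0.2812 is the smallest difference detectable with 90% power, not the expected gap, and the protocol states no expected gap.
- **Local advertisement may be partly offline.** The protocol gives no split between that and social media. Completion is still online.
- **Some analysis detail belongs in the analysis plan.** Section 2.4.2 defers a detailed plan until WP1 is complete, so the absence of mode-restricted sensitivity analyses is not itself a fault.

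None of this removes the asymmetry: offline adults can enter one group and not the other.

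**Conclusion.** The concern holds as a design point about the referent group's mode of completion. The referent mean is probably inflated and the inequality estimate probably overstated. The direction rests on offline adults scoring lower on a measure that includes digital access, use and skills, and on selection in the intellectual-disability sample not cancelling the effect. The amount cannot be derived from the protocol. The range of 0.02 to 0.30 SD is illustrative, from an assumed excluded share of 2% to 15% scoring 1 to 2 SD lower, before any reduction by weighting. At the low end the effect is negligible; at the high end it matches the planned detectable difference. The sample-size statement is correct and is not affected.

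**What to change.** 1. Amend section 2.4.2 so that referents may complete the survey on paper or by telephone, using the options already planned for the other group.
2. State there that local advertisement includes general community outlets offline. Partner-organisation venues should not be used for this: they are mainly advocacy organisations for people with intellectual disabilities, and the non-disabled adults found there are likely to be staff, carers and relatives.
3. Record completion mode and reporter (self, supported, proxy) for every participant.
4. Add a sensitivity comparison restricted to online self-completers in both groups. It answers a narrower question, but on like terms.
5. If online-only completion is kept, word the conclusion as a comparison with non-disabled adults who are online. This costs nothing.

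Cost of items 1 to 4: an amendment, printing and postage, some existing researcher time, and possibly slower referent accrual than the planned 25 to 30 per month. The researchers' time is not free, since they also support two survey waves and the weekly diary check-ins. No sample size changes.

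### The 90% power at d=0.2812 is for an unweighted t-test and makes no allowance for the planned inverse-probability weighting, and the fallback from weighting is tied to a convergence failure that a weighted linear model does not show

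*Protocol*

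**What the plan says.** Protocol section 2.4.2 sets the size of the referent group: "A referent sample of 200 will allow detection of a group difference, $d=0.2812$ (small-medium effect) at 90% power, 2:1 group ratio". Alpha is 0.05, the software is G*Power, and neither the test nor its sidedness is named. The group sizes are given in sections 2.4.2 and 2.4.1: "A reference group of 200 participants without disabilities will be recruited across the study sites via local advertisement and social media" and "a self-selecting sample of 400 adults with intellectual disabilities will be recruited equally from the four study sites".

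The analysis part of section 2.4.2 plans a general linear model and adds: "The study will use propensity score weighting (inverse probability weights) to reduce the bias due to confounding variables". The propensity variables are region, sex, age band, ethnicity and deprivation index. One circumstance for changing method is given: "In the event that models including the probability weights do not converge, we will explore other approaches to resolve". Direct covariate adjustment is the example offered.

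**The concern.** The sample size paragraph and the analysis paragraph of the same section describe different estimators. Unequal weights reduce the effective sample size, mostly in the smaller referent group, and the calculation leaves no reserve. If that loss is not recovered elsewhere, the comparison that answers the inequality part of the primary aim has less than its advertised power.

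The fallback rule looks for the wrong event. Weighting usually goes wrong through extreme weights, poor overlap or residual imbalance. None of these stops a weighted linear model from returning an answer, so a noisy or still-imbalanced estimate could stand as the main result with the stated trigger never met.

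**Working it through.** **Inputs.** From the protocol: n = 200 and 400, alpha 0.05, power 90%, d = 0.2812. Two-sided testing is assumed because sidedness is not stated. The variance inflation from weighting (DE) is not in the protocol and is assumed here.

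**Step 1: reproduce the stated figure.** For an unweighted two-sample t-test the non-centrality is d × √(n1·n2/(n1+n2)) = 0.2812 × √(200 × 400/600) = 0.2812 × 11.547 = 3.247, with 598 degrees of freedom. Power is 0.9000, and the d that gives exactly 90% is 0.28118, which rounds to 0.2812. A one-sided test would give 0.2537, which does not match. The figure is therefore the unweighted two-sided test with nothing added.

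**Step 2: allow for weighting.** Divide both group sizes by DE, with covariates unrelated to the outcome. The detectable difference is then about 0.28118 × √DE.

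| Assumed DE | Effective n | Power at d=0.2812 | Detectable d at 90% |
|---|---|---|---|
| 1.0 | 200 / 400 | 90% | 0.281 |
| 1.1 | 182 / 364 | 87% | 0.295 |
| 1.25 | 160 / 320 | 83% | 0.314 |
| 1.5 | 133 / 267 | 75% | 0.345 |

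**Step 3: relate DE to imbalance.** A simulation of the weighted linear model used robust standard errors, 1,500 replicates and four normal covariates unrelated to the outcome. Two covariates were shifted between groups, by s and s/2 SD.

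| s (SD) | Referent effective n | Power |
|---|---|---|
| 0 | 197 | 91% |
| 0.25 | 190 | 87% |
| 0.5 | 170 | 86% |
| 0.75 | 137 | 80% |
| 1.0 | 102 | 70% |

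**Step 4: the fallback trigger.** With weights W fixed, the general linear model estimate is (X'WX)⁻¹X'Wy. There is no iteration, so there is nothing to converge. Every weighted fit in the simulations returned an estimate. In a separate simulation with three covariates each shifted by 0.5 SD, 12–14% of datasets still had a standardised difference above 0.1 after weighting, and none of them would have met the stated trigger.

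**The case against.** **The loss is not established.** This is the strongest objection, and it stands. A reader might infer that the planned analysis certainly has less than 90% power. The documents do not support that. The protocol gives no imbalance, no weight type and no design effect. The propensity variables are chosen as confounders, so they are presumed to predict the outcome, and weighting on an estimated score can then gain precision. With three covariates, weights targeting the whole population, assumed covariate R² of 0.2–0.3 and a variance that accounts for the estimated score, simulated power was 92–95% at 0.3 SD imbalance per covariate and 90–91% at 0.4 SD. The recovery has limits: power was 84–86% at 0.5 SD, and treating the weights as fixed gave 88–89% at 0.3 SD and 82–84% at 0.4 SD.

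**Imbalance is not certain either.** A reader might infer it from targeted recruitment of older and ethnic-minority people with intellectual disabilities. Section 2.4.1 makes that step conditional on insufficient representation at review. Region is near-balanced by design, and the logic model in Appendix 1 calls the referent group matched, although no matching method is given. What remains is that the two groups are recruited by different routes: advertisement and social media for referents, partner organisations and an NHS trust for the others.

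**Diagnostics belong in the statistical analysis plan.** Section 2.4.2 promises one, and thresholds can properly wait for it. The protocol also names balance as a purpose of the weighting, so it cannot be read as ruling out balance checks. But the power claim and the trigger are already written, and both are open to criticism as they stand. The logistic propensity model could fail to converge through sparse cells, but the wording refers to models that include the weights.

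**Conclusion.** The point holds in a limited form. It is certain that 0.2812 is the unweighted figure and carries no allowance for weighting. It is also certain that the stated trigger cannot detect poor balance or extreme weights in a linear model.

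The size of any power loss is an assumption. It is about 3, 7 or 15 percentage points for inflation of 1.1, 1.25 or 1.5 if the covariates explain none of the outcome, and possibly nothing if they are prognostic and imbalance is mild. Even at inflation of 1.5 the detectable difference rises only from 0.281 to 0.345. The range 0.295–0.345 describes the weighted model without covariate adjustment. It should not be quoted as the figure for a weighted model that also adjusts for them.

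**What to change.** 1. Label 0.2812 in section 2.4.2 as the unweighted figure and add the detectable difference over a stated range of assumed weighting inflation, for example 0.295 to 0.345 for inflation of 1.1 to 1.5 without covariate adjustment.
2. Make the primary analysis the weighted general linear model with the five propensity variables also in the outcome model, with robust standard errors. In a simulation with R² of 0.2, this raised power from 81% to 88% at 0.4 SD imbalance and from 76% to 87% at 0.5 SD.
3. Replace non-convergence with a pre-specified check of post-weighting balance and effective sample size. Keep direct adjustment, which the protocol already names, as the alternative. The sponsor sets the thresholds, before outcome data are seen. A switch to overlap weights is debatable because it changes the target population.

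The cost is a slightly less favourable stated figure and a little more analysis work. The five variables are already needed for the propensity score, and no extra participants are required.

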Descriptive analysis of levels and frequency of digital health participation. A cross-lagged path analysis (CLPM) will investigate changes over time and identify causal relationships between aspects of digital health participation and physical and mental wellbeing, while controlling for demographic and background characteristics (Kenny & Harackiewicz, 1979). By fitting the model with causal crossed lagged pathways in both directions, we can address whether aspects of digital health participation causally precedes physical and mental wellbeing or vice versa in individuals with intellectual disabilities. Sample sizes $N=100 - 400$ are sufficient for structural equation modelling; more specifically, $N=150$ for models including seven or fewer variables with modest communalities (below 0.5) and zero under identified constructs (Hair *et al.*, 2014). We will fit models with and without cross lagged effects and use likelihood ratio tests (specifically, AIC and BIC criterion) to compare these nested models to determine which better fits the data (Kenny & Harackiewicz, 1979). If data is found to be missing at random (MAR), CLPM analyses will default to using full-information maximum likelihood. All models will be reported with robust standard errors and model fit will be evaluated using the comparative fit index (CFI >0.9), Tucker-Lewis Index (TLI >0.9), standard root mean squared residual (SRMR <0.08) and root mean square error of approximation (RMSEA <0.08), (see Wang & Wang, 2012; Hu & Bentler, 1999; Schreiber *et al.*, 2006).

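### Section 2.4.2 admits the five covariates to the primary outcome model only if a weighted linear model fails to converge, which it almost never will

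*Protocol*

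**What the plan says.** Protocol section 2.4.2 compares people with intellectual disabilities (400) with a referent group (200). Digital health participation is the primary outcome. The analysis is given as "Between group comparison using general linear model (GLM) of digital health participation of people with intellectual disabilities". No list of model terms follows.

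Confounding is handled by weights: "The study will use propensity score weighting (inverse probability weights) to reduce the bias due to confounding variables and ensure sufficient balance across groups". The variables are "geographic region, sex, age band, ethnicity, and deprivation index".

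The same variables may enter the outcome model under one condition: "In the event that models including the probability weights do not converge, we will explore other approaches to resolve (i.e. direct adjustment", justified by "direct adjustment as the number of covariates is relatively small".

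On precision, 2.4.2 says "All parameter estimates will be reported with 95% confidence intervals" and leaves further detail to a later SAP. Sections 2.3.5 and 2.4.1 do state a variance method, "All models will be reported with robust standard errors", but each time in the same sentence as fit indices for the factor and cross-lagged models.

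**The concern.** The protocol fixes an order: weight first, and adjust directly only if the weighted models do not converge. The natural reading is that the weighted model does not already hold the covariates, since otherwise direct adjustment would not be another approach. The condition for moving to adjustment is close to empty for a linear model. A SAP that follows the protocol would inherit the order.

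Two things are at stake for the primary outcome. First, the interval depends heavily on a variance estimator that 2.4.2 does not name. Second, with the covariates left out, even the usual robust interval is wider than it need be when those covariates predict the score. The five variables have to be collected for the weights, so using them costs nothing in data.

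**Working it through.** **1. The plan's own figure.** Inputs from 2.4.2: 200 referents, 2:1 ratio, alpha 0.05, 90% power. The exact noncentral t for 400 v 200, two-sided, gives power 0.9000 at d = 0.2812, and solving for size returns 200. It reproduces. In SD units the unweighted standard error is √(1/400 + 1/200) = 0.0866.

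**2. The trigger.** With design matrix D and weights W, the estimate is (DᵀWD)⁻¹DᵀWy. There is no iteration, so nothing has to converge. The logistic propensity model could fail, but then there are no weights, and the condition speaks of models that include them.

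**3. Default errors, no imbalance.** The protocol does not say whether weights are stabilised, so both are shown.
- Unstabilised (1/p): weights sum to about 600 in each group and the weighted residual variance is about 1200σ²/600 = 2σ². Default variance = 2σ²(1/600 + 1/600) = σ²/150, SE 0.0816σ. If covariates do not predict the outcome, the true variance is at least σ²(1/400 + 1/200) = σ²/133. Ratio 0.0816/0.0866 = 0.943; coverage 2Φ(1.96 × 0.943) − 1 ≈ 93.5%.
- Stabilised: weights are about 1, the default variance is σ²/133, and simulated coverage was 95.2%.

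**4. Default errors, uneven weights.** Assume moderate confounding with effective sizes 385 and 171. The true SE is √(1/385 + 1/171) = 0.0919, the ratio is 0.0816/0.0919 = 0.888, and coverage is about 92% (simulated 92.5%).

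**5. Simulation with all five variables** (400 v 200, 1,500 runs per row, plain sandwich errors without a leverage correction). Confounding strength, prognosis and estimand are assumptions; the protocol gives none. All variables except region act through a score with variance 0.6²×0.25 + 0.4²×1.25 + 0.6²×0.1275 + 0.3²×2 = 0.516. A coefficient b on it therefore explains 0.516b²/(0.516b² + 1) of the outcome variance: 11%, 34% and 67% for b = 0.5, 1 and 2.

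| Weights, confounding | Explained | Effective n | Group only, default | Group only, robust | With covariates, robust |
|---|---|---|---|---|---|
| Whole population, mild | 0% | 395/189 | 93.5% | 95.5% | 95.1% |
| Whole population, mild | 34% | 395/189 | 96.3% | 97.8% | 94.7% |
| Whole population, moderate | 67% | 385/171 | 99.7% | 99.9% | 95.7% |
| Whole population, strong | 0% | 340/113 | 84.7% | 94.6% | 93.0% |
| Intellectual-disability group as target, strong | 11% | 400/75 | 78.5% | 94.8% | 90.8% |

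**6. Simulations with two covariates** (no true gap, 1,500 or 2,000 runs per scenario, HC3 errors; imbalance, prognosis and SDs assumed).
- Default errors, 0.5 SD imbalance, unrelated covariates, equal SDs: 90.1% to 90.8%.
- The same with SD 0.8 in the intellectual-disability group v 1.2 in referents: 86.3% to 89.0% in separate runs, and about 87% with stabilised weights.
- Default errors, about 30% explained, SD 1.2 v 0.8: 96.9% to about 98%.
- Default errors, 0.5 SD imbalance, 30% explained, equal SDs: 95.3%.
- Group only, HC3, prognostic covariates: 97.8% to 98.5%.
- Weights plus covariates, HC3: 94.4% to 96.2% in all scenarios tried.

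**7. Width of the reported interval.** With 30% explained, the SE with covariates was 0.081, against 0.097 or 0.103 for weights-only robust errors in two sets of runs: 1 − 0.081/0.097 = 16% and 1 − 0.081/0.103 = 21% smaller. With nothing explained it was 0.097 v 0.096 and 0.096 v 0.096. Most of the gain is in reporting. Coverage of 97.8% to 98.5% corresponds to |z| of 2.29 to 2.43, so the weights-only robust SE is about 1.17 to 1.24 times the true one, and 0.103/1.24 to 0.103/1.17 is 0.083 to 0.088. The weights already deliver much of the precision; the weights-only interval does not show it.

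**The case against.** A reader might infer that the protocol prescribes a group-only model with ordinary intervals. It does not. No sentence lists the model terms; the absence of covariates is inferred from the fallback wording. Section 2.4.2 promises 95% intervals without naming an estimator, and the robust errors promised for the neighbouring models give no ground for assuming default ones here. Terms, weight type and variance method are ordinary SAP content, and 2.4.2 announces a SAP, so silence on them is not an error.

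A reader might also take a coverage range as a property of the plan. It is not: the low two-covariate figures combine sizeable imbalance, unequal spread and covariates unrelated to the outcome, and such covariates are not confounders. Other assumptions give about 78% to above 99%, and stabilised weights remove the defect when there is no imbalance.

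Finally, weights-only analysis with robust or bootstrap errors is legitimate, and adding covariates is partly a preference. In the strongest-confounding row above, weights-only robust coverage (94.8%) was nearer nominal than the adjusted figure (90.8%).

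All of this stands. It does not touch the ordering, which is stated: adjustment waits on an event that a linear model essentially cannot produce.

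**Conclusion.** The point holds as a weakness in the stated ordering. As written, the five covariates act through the weights and would almost never enter the primary outcome model. The consequence for intervals is conditional. If default errors were used, coverage of nominal 95% intervals could be roughly 87% to 98% in the two-covariate scenarios. If robust errors were used without covariates, intervals would be conservative when the covariates are prognostic. With covariates and robust errors, coverage was about 94% to 96% with two covariates and about 91% to 96% with all five, so exact nominal coverage should not be promised. The reported SE is about 20% smaller if covariates explain about 30% of the outcome variance, and essentially unchanged if they explain nothing. Every one of these figures rests on assumed imbalance, prognosis, spread and estimand. The sample size and power (d = 0.2812, 90%) are sound as stated.

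**What to change.** In section 2.4.2:
- Make the primary analysis the weighted general linear model of the participation score on group plus the same five covariates, with heteroscedasticity-robust (HC3) standard errors, in line with the robust errors already promised in 2.3.5 and 2.4.1. Pool by Rubin's Rules where data are imputed.
- Delete non-convergence as the condition for entering the covariates.
- Report the weights-only estimate as a sensitivity analysis.
- Let the SAP name the target population of the weights and say whether they are stabilised.

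The cost is a few sentences and a few lines of code, with no new data. The downside is slight extra dependence on the form of the covariate terms, which the sensitivity analysis makes visible.
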